In addition, quantitative measure of hand opening area and closing force (QMHOc) will be conducted during the whole course of 12-week home-based practice, using pressure sensors (Pressure Profile Systems, Inc., Los Angeles, CA 90045) in conjunction with portable Moire Phase Tracking cameras (Metria Innovation, Inc., Wauwatosa, WI) (~1 hour).

F. Study Design and Methods

F.1. Lab-based testing

Each PT will be trained for the use of ReIn-Hand by watching a 20-min video, and practice the use of ReIn-Hand under the supervision of the research PT, [name], who is experienced in using ReIn-Hand device.

F.1.1. A. Pre-training non-EEG Experimental protocols

Once confirmed, a stroke participant will be randomly assigned to one of 11 physical therapists (10 clinical PTs+1 research PT (i.e., [name])) who will participate this study. The assigned PT will determine 1) the electrode positions for recording the muscle activities during performing different arm/hand function, and 2) the stimulation electrode positions and stimulation intensities for

achieving the best hand opening with the forearm at 0° and 90° positions (~1-1.5 hour). Then, the corresponding electrode positions will be marked, and the forearm/hand with these markers will be scanned (~0.5-1 hour). This visit is expected to last approximately 3 hours. The scanned results will be used to develop a subject-specific forearm-hand orthosis (FHO) that fits to the paretic forearm and hand.

B. Pre-training EEG Experimental protocols

Before and after this 12-week home-based practice, these stroke individuals will participate in an electroencephalography (EEG) experiment. Additionally, 10 control subjects will be recruited to participate in one session of this EEG experiment to provide healthy neuroimaging data for comparison.

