After the subject-specific FHO is ready, the stroke participant and his/her paired PT will be called to participate the 1st and 2nd lab-based training with ReIn-hand device. During these 2 visits, the assigned PT (1st test) or the research PT (2nd test) will train the stroke participant to use his/her FHO and the ReIn-Hand software on a mobile phone, until the stroke participant demonstrates the ability in using the device independently twice in a row. On the 2nd test, the research PT will also re-test partial of the clinical assessments, however, this time with the assistance of ReIn-Hand device. Each of these 2 visits is expected to last about 3 hours. During these 2 visits, we will measure the time for a stroke participant to learn the use of ReIn-Hand device. Within 0-3 days after the 1st (for PTs) or the 2nd lab-based training (for individuals with stroke), a 5min user survey to report the level of ease-of-use of the ReIn-Hand device will be conducted.

[figure not shown]

Figure 4. EEG Experimental setup showing a subject using the ACT^{3D} robot while high-density EEG and surface EMG signals will be simultaneously recorded. Visual feedback will be displayed on a computer screen.

F.2. Home-based practice

After the 3 lab-based visits as listed above, 4 out of 20 stroke participants will further participate the home-based practice. They will take the ReIn-Hand device, including his/her FHO, the mobile phone with ReIn-Hand software, and the electronic stimulator (300 PV, Empi, Minnesota, USA, a FDA approved clinical device) back to home. At home, they will perform 20 trials of pre-set tasks, like reaching and grasping, per session (1 hour), 1 session per day, 7 days per week for 12 weeks. During these 12 weeks, they will visit the lab once per week to make necessary device changes, update the partial of the clinical assessments, all without ReIn-hand. These clinical tests will also be re-measured at 1 and 3-month after the home-based practice, again without ReIn-hand.

Both electrodes and electrical stimulator are commercially available devices (300 PV Complete Electrotherapy System, Empi, Inc., St. Paul, MN). Each subject will be assigned task-specific, functional exercises targeted to their individual abilities, deficits, and personal preferences. Stimulation will be provided with the following characteristics:

Amplitude – at motor threshold with the maximum intensity lower than 100 mA
 Frequency – $50\pm20\%$ Hz

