Cortical activity related to hand open with and without lifting	We will use EEG data to estimate the cortical activity related to the 2 motor tasks pre- and post-home-practice	Post-intervention cortical activity related to these 2 motor tasks become 'closer to' that in healthy control subjects.

¹Ease-of-use feature of the device will be reflected by the <3 hours learning time. We will further study effects of 1) PT's experience with ReIn-Hand, and 2) the number of experimental sessions on the time to learn to use the device. For PT's experience, since [name] already has 4-year experience in using current ReIn-Hand device in stroke participants, we will compare 1) the learning time on day 2 of the group 1 (N=10) working with the 10 PTs versus the time of the group 2 (N=10) working with [name]; and 2) the learning time of group 1 on day 2 with the 10 PTs versus the time of the same group on day 3 with [name]. A non-significant difference for both comparison will suggest non-significance for PT's experience in using the device. For the number of sessions needed to learn to use the device, we will compare the learning time of both groups on day 2 versus that on day 3. A non-significant difference will suggest sufficiency of one session in learning the device.

Evaluation of the usability of the ReIn-Hand: Within 0-3 days after Day 3, the 10 PTs and the 20 stroke participants will finish a 5min user survey to report the level of ease-of-use of the ReIn-Hand device. Items that will be rated (on ordinal scale 0-5, with the easiest use at 5) include: 1) determination of the stimulation/recording electrode positions (PT only), 2) setting up the initial detection rule (PT only), 3) fine adjustment of the detection rule (both), 4) placement of the FHO (both), 5) using the mobile phone software (both), 6) performance of the trained functional task (both). We expect to observe users' grades $\geq 4/5$, with grades $\leq 3/5$ will be queried for explanation and compiled for future design modifications.

Transportation: Participants will be given reimbursement for transportation expenses. Participants are encouraged to take public transportation, or to drive and park in Northwestern Medical School parking lots (located at [name] or [name]) where a parking sticker

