Official Title of the Study: Development of a FES Device for Hand Use During Arm Activities Following Stroke

NCT03986216

October 26, 2020

For each of the surveyed questions (scaled from 1-5 with 1 representing the no satisfied and 5 as very satisfied), we will calculate the mean and standard deviation, with a focus on identifying scores < 3/5.

We will use single and paired T-tests to determine the effects of PT experience and the number of training sessions on participant satisfaction, respectively.

We will use the repeated measure of ANOVA to test whether the training session number plays a role in the hand function as primarily measured by Box and Blocks Test and the other secondary measures.

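### Two non-significant comparisons cannot show that PT experience has no effect, because the experienced side is one research PT and each test has only 10 participants per group

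*Protocol*

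**What the plan says.** Footnote 1 to Table 3 (Protocol F.3) studies whether a PT's experience with the device affects the time a stroke participant needs to learn it. Experience is represented by one research PT, who "already has 4-year experience in using current ReIn-Hand device in stroke participants". There are two comparisons:

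- **Comparison 1, between participants:** "the group 1 (N=10) working with the 10 PTs versus the time of the group 2 (N=10) working with" the research PT.
- **Comparison 2, within participants:** "the learning time of group 1 on day 2 with the 10 PTs versus the time of the same group on day 3 with" the research PT.

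The decision rule is: "A non-significant difference for both comparison will suggest non-significance for" PT experience. The footnote names no statistical test and no margin. Its days 2 and 3 appear to be Days 3 and 4 of Tables 2 and 3, where the device-use timings are listed.

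Section F.1.1 describes the therapist pool: each participant is "randomly assigned to one of 11 physical therapists (10 clinical PTs+1 research PT". Section F.1.2 fixes who trains when: "the assigned PT (1st test) or the research PT (2nd test) will train the stroke participant".

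The SAP is brief: "We will use single and paired T-tests to determine the effects of PT experience and the number of training sessions on participant satisfaction, respectively". It does not define the experience groups, has no therapist term and does not mention learning time.

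**The concern.** The footnote draws a conclusion about a general attribute, experience with the device. The design compares ten clinical PTs with one particular person, who may teach faster or slower than others for reasons unrelated to four years of use. The same person is the experienced side of both comparisons, so the second does not check the first independently.

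The rule also treats two non-significant results as evidence of no effect, in groups of 10 and with no statement of how small a difference would count as none.

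Learning time is the first measure in Table 3. A finding that PT experience does not matter would be read as support for handing the device to clinicians who are new to it. The planned data cannot support that reading.

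**Working it through.** **Inputs from the documents.** Comparison 1 has 10 versus 10 participants, and comparison 2 uses the same 10 participants twice (footnote 1). There is one experienced therapist (footnote 1), who trains everyone at the second visit (F.1.2). The group sizes are taken from the footnote. Equal-probability assignment among 11 therapists, one reading of F.1.1, would give the research PT only 20/11 ≈ 1.8 of 20 participants, so those two places need reconciling.

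**Inputs not in the documents, assumed here.** Two-sided 5% level; normal data; effects in SD units (d). The plan gives no power, SD or margin, so there is no stated figure to reproduce.

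**Step 1: what each comparison estimates.**

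| Comparison | Difference measured | Mixed in with experience |
|---|---|---|
| 1 | clinical PTs − research PT, first training visit | the individual research PT |
| 2 | clinical PTs at first visit − research PT at second visit | the individual research PT, and first versus second session |

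Write E for the effect of experience, P for the research PT's personal deviation from other equally experienced PTs, and S for the session effect. Comparison 1 estimates E + P and comparison 2 estimates E + P + S. With one experienced PT, E and P never appear apart. A result near zero can mean no effect of experience, or an effect cancelled by P (or by P + S). A clear difference can equally be P or S alone.

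**Step 2: how much non-significance would show.** For comparison 1, the noncentral t distribution with 18 degrees of freedom and noncentrality d × √(10/2) gives:

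| True d | Power | Chance of a non-significant result |
|---|---|---|
| 0.5 | 19% | 81% |
| 0.8 | 40% | 60% |
| 1.0 | 56% | 44% |

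Power of 80% needs d ≈ 1.32. The 95% confidence interval has half-width 2.101 × √(2/10) = 0.94 SD, so even an observed difference of zero leaves differences of up to about 0.9 SD in either direction compatible with the data.

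**Step 3: the rule as a whole.** Both comparisons must be non-significant. Simulation assumed a within-participant correlation of 0.5, no session effect and no differences between individual therapists, which is favourable to the plan. The rule would still point to no effect of experience in about 61% of studies when the true effect is d = 0.5, and in about 28% when it is d = 0.8.

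**Step 4: illustration of why the result does not generalise.** Suppose a share ρ of the variance lies between therapists (ρ is assumed; the documents give none), and each clinical PT has one participant (inferred from 10 participants and 10 PTs). For a claim about experience in general, the variance of the comparison 1 difference is (2 + 9ρ)/10. An ordinary t-test estimates (2 − ρ)/10. The ratio of standard errors is √[(2 + 9ρ)/(2 − ρ)].

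| ρ | SE ratio | False-positive rate of a nominal 5% test |
|---|---|---|
| 0.05 | 1.12 | about 7.7% |
| 0.10 | 1.24 | about 10.6% |
| 0.20 | 1.45 | about 16.5% |

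More participants with the same person would not remove this: the research PT's own contribution to the variance stays at ρ.

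**The case against.** The strongest counter-argument is that the comparison is legitimate if read for what it is. With the research PT as a fixed comparator, the variance is 1/10 + (1 − ρ)/10 = (2 − ρ)/10, which is what the t-test estimates, and simulation keeps the false-positive rate at about 5%. This stands. It is the reason for renaming the contrast, and it means no variance inflation is needed once the contrast is renamed.

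A reader might infer from step 4 that the planned t-test is invalid because its standard error is too small. The documents do not support that stronger reading, for three reasons. The inflation arises only if the result is generalised beyond this person, and its size depends on a ρ that nobody has stated. It concerns false differences, whereas the plan's only rule concerns non-significance, which a too-small standard error makes harder to reach. And the SAP names its t-tests for satisfaction, while footnote 1 names no test for learning time.

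Other points have some weight. All PTs watch the same training video and practise under the research PT (F.1), which may narrow differences in teaching. The footnote's verb is cautious. The ease-of-use criterion itself is a learning time below 3 hours, and PT experience is a further question in a 20-participant device study. These limit the importance of the point, but none of them separates experience from the individual. Comparison 2 does not do so either, since it uses the same person and adds session order.

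**Conclusion.** The point holds as one about interpretation. The design can compare this research PT with the clinical PTs. It cannot attribute a difference, or the lack of one, to experience, and comparison 2 also carries the session effect. This follows from the documents without any assumption. The SAP's test of PT experience on satisfaction has the same limit if it uses the footnote's groups, the only such grouping described.

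Separately, non-significance would be weak evidence of no effect. Power is about 40% at d = 0.8, the interval half-width is about 0.94 SD, and there is no equivalence margin. These figures assume a two-sided 5% level and normal data. The 61% for the whole rule at d = 0.5 also assumes a within-participant correlation of 0.5, no session effect and no therapist variation.

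The figures in step 4 are an illustration under an assumed ρ, not a measured defect of the test. The study can proceed, but the stated conclusion should change.

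**What to change.** In footnote 1 and the SAP:

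1. Rename the contrast as research PT versus clinical PTs.
2. Delete the rule that non-significance in both comparisons suggests no effect of PT experience.
3. Report each difference with a 95% confidence interval.
4. State that comparison 2 is also confounded with session order, because the research PT always trains second.

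No sensitivity table with inflated variance should be added; it would give intervals too wide for the renamed contrast.

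The cost is a few lines of wording and a narrower claim: the trial would report how learning time differed between this research PT and the clinical PTs, and would say nothing general about experience. No added therapist, participant or visit is needed.

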Official Title of the Study: Development of a FES Device for Hand Use During Arm Activities Following Stroke

NCT03986216

October 26, 2020

For each of the surveyed questions (scaled from 1-5 with 1 representing the no satisfied and 5 as very satisfied), we will calculate the mean and standard deviation, with a focus on identifying scores < 3/5.

We will use single and paired T-tests to determine the effects of PT experience and the number of training sessions on participant satisfaction, respectively.

We will use the repeated measure of ANOVA to test whether the training session number plays a role in the hand function as primarily measured by Box and Blocks Test and the other secondary measures.

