Throughout the experiment, we will measure scalp recordings using a 160-channel EEG system using active electrodes (Biosemi, Inc., Active II, Amsterdam, The Netherlands). Surface EEG electrodes will be mounted on a stretchable fabric cap based on the 10/20 system. The cap will be fitted on the head of the subject with the Cz electrode aligning with the intersection of the planes defined by the nasion, inion, and pre-auricular points. Eye movement detection electrodes will also be placed on the supra- and infra-orbital margins for detection of vertical eye movement. The skin under each electrode site will be prepared by clearing away any hair, and conductive gel

will be injected to achieve electrode impedances lower than $5\text{k}\Omega$ throughout the experiment. EEG data will be collected at 2048 Hz sampling rate and anti-aliasing filter (100 Hz) will be provided before data acquisition. The Biosemi system is equipped with active electrodes that provide a first amplification stage, allowing detection of EEG signals with a higher SNR and quicker preparation. A Polaris Krios handheld scanner and reflective markers (NDI, Ontario, Canada) will be used to record the EEG electrode positions compared to the coordinate system defined by the nasion, inion, and pre-auricular notches. EMG will be recorded from the extensor carpi radialis, flexor carpi radialis, and deltoid of the arm. The EEG and EMG data will be collected and stored on a computer.

These sessions will allow us to compare the cortical activity related to these movements pre- and post-intervention for the stroke individuals and how these compare to healthy controls to investigate any intervention-induced cortical reorganization.

F.1.2. The 1st and 2nd lab-based training with ReIn-Hand (2 visits)

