 Pulse Duration – 300-400 microseconds
 Ramp/Fall Times and Duty Cycle – adjusted to the task

F.3. Data collection and procession

Main data collection is listed in table 2.

Day 1	#1, Demographic data, #2, Clinical assessments as listed above, #3, Time for a) determining the stimulation /recording electrode positions, b) for scanning,
Day 2	#1, EEG data, #2, EMG data, #3, finger position during hand-opening and graping force data during closing
Day 3	#1, Time for the stroke subject to a) to attach the FHO, b) use the software, including connecting all the cables following the instructions, c) set up the detection rule, and d) clean up. #2, The accuracy in detecting grasping and releasing; and #3, EMG data while performing task, sampled at 1K Hz.
Day 4	Measures #1-3 on Day 2, #4, ARAT and BBT with the assistance of ReIn-Hand.
Home-based test	Measures #1-4 on Day 3 and MAL-14, NSA, and hand opening and closing ability weekly during the 12-week home-based practice, then again at 1 and 3-month after. To the end of the 12-week home-based practice, we will use a GLOC scale (one question survey) to collect user overall satisfiaory level of the ReIn-Hand supported home practice.

Data analysis for evaluating the engineering aspects is listed on Table 3.

Primary measures	Measured by	Expectation
Time for learn-to-use the device	#1 on Day 3 and Day 4	<3 hours in each of the 2 days, and no difference between 2 days ¹ .
Time for setup and cleanup	#1 a) and d) on Days 3 & 4, and during the home-based test	<5 min for each, and significantly less than the

		measure #3 (a) on Day 1
Successful rate on controlling grasping and releasing during reaching	#2 on Days 3, 4, and during the home-based test	a false 'transfer' < 10%
Time delay caused by the device	We will detect the onset of EMG at the extensor measured on days 3 &4, and the onset of stimulation artifact. The latency between them will be calculated.	<350 ms
Difference in Clinical assessments with and without ReIn-Hand	Difference between measure #4 on Day 4 & measure #2 on Day 1	ARAT and BBT with ReIn-Hand will outperform that without ReIn-Hand.
Willingness to use ReIn-Hand at home	#1-3 during the home-based test	Continuous use on daily base.

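### In the 20 participants the SAP's session test on Box and Blocks is fully confounded with device assistance; any longer series is 4 people, with an unresolved test list and device condition

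*SAP*

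**What the plan says.** The SAP's only hand-function analysis is one sentence: "We will use the repeated measure of ANOVA to test whether the training session number plays a role in the hand function", measured primarily by BBT and also by unnamed secondary measures.

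The protocol places BBT as follows.

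- **Day 1 (E.2; F.3, Table 2).** BBT is in the pre-training battery for everyone.
- **Day 3, first lab training (Table 2).** The row has items #1 to #3 (times, detection accuracy, EMG) and no BBT.
- **Day 4, second lab training.** F.1.2 has the research therapist "re-test partial of the clinical assessments, however, this time with the assistance of ReIn-Hand device". Table 2 lists "Measures #1-3 on Day 2, #4, ARAT and BBT with the assistance of ReIn-Hand".
- **Home practice (F.2).** "4 out of 20 stroke participants will further participate the home-based practice". Weekly lab visits "update the partial of the clinical assessments, all without ReIn-hand", and these tests are "re-measured at 1 and 3-month after the home-based practice, again without ReIn-hand". F.2 does not say which tests.
- **Home practice (Table 2).** The home row points to measures #1 to #4 of Day 3 and adds MAL-14, NSA and hand opening and closing, weekly for 12 weeks and again at 1 and 3 months.

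Table 3 takes measure #4 on Day 4 minus measure #2 on Day 1 as the comparison of clinical scores with and without the device.

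**The concern.** A repeated-measures test of session number needs the same measurement, under the same condition, at several sessions. The 20 participants do not have that for BBT. If the test is run on the two scores they do have, a benefit of wearing the device could be reported as a benefit of training. If it is run on the home phase, it rests on 4 people, and the choice of visits and device condition is left open until the data are in hand.

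The lab reading is a natural one. The SAP's preceding sentence and the Table 3 footnote both discuss the number of sessions in connection with the lab training visits.

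**Working it through.** **Step 1: BBT scores in the 20.** The documents state no sample-size or power figure for this test, so there is none to reproduce. The count comes from E.2, F.1.2 and Table 2.

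| Visit | Training sessions begun | Device | BBT |
|---|---|---|---|
| Day 1 | 0 | no | yes |
| Day 3 | 1 | not applicable | none |
| Day 4 | 2 | yes | yes |

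With two occasions the ANOVA equals a paired t-test, F(1,19) = t², with critical value 4.38 at an assumed two-sided 5%. Its one contrast is

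mean(Day 4 − Day 1) = session effect + device effect.

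There are two unknowns and one equation. Each device condition has one score, so there is no within-condition repeat across sessions. The same contrast appears in Table 3 as the device effect.

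**Step 2: the home-phase reference.** Day 3 has no #4; only the Day 4 row does. Four other places are consistent with day numbers left unchanged when the EEG visit became Day 2:

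- F.2 counts 3 lab visits before home practice, while Table 2 lists four days.
- The Day 4 row repeats measures #1 to #3 of Day 2, the EEG day; moved one day, this is the Day 3 list.
- The Table 3 footnote compares learning times on days 2 and 3, while the table body uses Days 3 and 4.
- The usability paragraph places the stroke survey after Day 3, while F.1.2 places it after the second training, now Day 4.

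Moved by the same one day, the home row points to Day 4 items #1 to #4, which include ARAT and BBT **with** the device. F.2 says the home-phase tests are **without** it. The best-supported repair supplies BBT but leaves the device condition in conflict.

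**Step 3: if BBT is weekly in 4 people.** Assumed here: n = 4; k = 13 (baseline plus 12 weeks); nominal 5%; normal data; no true session effect. Degrees of freedom are (k−1) = 12 and (k−1)(n−1) = 36. The contrast covariance has rank n−1 = 3 for 12 contrasts, so no multivariate test exists and the sphericity correction is poorly estimated. Rejection rates from 40,000 simulations per scenario:

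| AR(1) correlation | Uncorrected | Greenhouse-Geisser | Huynh-Feldt |
|---|---|---|---|
| 0.5 | 8.3% | 0.2% | 6.2% |
| 0.7 | 11.3% | 0.6% | 7.7% |
| 0.8 | 13.2% | 1.0% | 8.5% |
| 0.9 | 15.0% | 1.7% | 8.9% |

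With k = 12 the rates are within about 1 point of these. With k = 15 (adding the two follow-ups) and correlation 0.9 the uncorrected rate is about 16%. Under compound symmetry the uncorrected test holds 5%. With only 4 occasions the uncorrected rate is about 6-7% and Huynh-Feldt about 5-6%, so the problem is small. A one-sample t-test on one slope or change per person holds about 5% throughout.

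**Step 4: sensitivity to normality.** The target population lacks hand function (section E), so unassisted BBT counts near zero are plausible. With illustrative Poisson counts, person means drawn from a gamma distribution around 0.3 to 3 blocks and no session effect, every test falls below 5%: the uncorrected ANOVA to roughly 1-4%, the t-tests to roughly 0.1-3%.

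**Step 5: width of the alternative.** The 95% half-width for a mean of 4 values is t(0.975, 3 df)/√4 = 3.182/2 = 1.59 SD of those values.

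**The case against.** The strongest reply has four parts.

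- **The SAP sentence is not confined to BBT.** It also covers secondary measures, and Table 2 makes MAL-14, NSA and hand opening and closing explicitly weekly. The ANOVA therefore has a series that needs no broken reference. This stands, but the series is still 4 people and the SAP does not say so.
- **The day-numbering slip is easy to read through.** One shift explains every anomaly, and F.2 then supplies the condition. The first half is persuasive as an inference. The second half does not settle the matter: the row reached by the shift specifies assisted BBT, and nothing says which text governs.
- **Greenhouse-Geisser protects the error rate.** It does. It was at most about 3% at 12 to 15 visits, including scenarios with person-specific trends. Its cost is power, not false positives.
- **The error rates depend on normal data.** They do, and Step 4 shows the inflation can vanish.

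A reader might also infer that the ANOVA cannot be run at all, or that no home-phase BBT is collected. The documents support neither. Two scores can be analysed; the fault is what the result means. Reading the Day 3 #4 as a slip for #3, which would remove home BBT, fits the other day-number anomalies least well.

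**Conclusion.** The point holds. In the 20 participants the stated BBT test cannot separate training session from device assistance; this follows from the visit schedule and needs no simulation. The only longer series is 4 of 20 people. For them the BBT schedule rests on a reference that cannot be followed as written, and Table 2's likeliest meaning conflicts with F.2 on device use.

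The error-rate point is conditional. If the series is weekly, the uncorrected ANOVA rejects about 8-16% and Huynh-Feldt about 6-9%, while Greenhouse-Geisser is very conservative at 0.2-1.7% (AR(1) 0.5-0.9, k = 13 for the two corrections). It would be wrong to conclude that both usual corrections inflate false positives. Alpha, covariance, number of visits and normality are all assumptions, and with near-zero counts the tests become conservative.

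The consequence is bounded: no Table 3 criterion depends on this test. What is at risk is how the Day 1 to Day 4 change is labelled and how the home-phase result is reported. The change should be made but is not critical.

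**What to change.** 1. Reconcile the day numbering in F.2, the Day 4 and home rows of Table 2, and the Table 3 footnote. The sponsor should confirm whether home-phase BBT is collected and in which device condition.
2. State in the SAP that the session analysis uses only the home-practice participants, at listed visits, in one device condition, and that Day 1 versus Day 4 is reported only as the device contrast.
3. If no home-phase BBT is collected, drop the BBT session test.
4. For weekly series (BBT if collected, and the weekly secondary measures), replace the omnibus p-value with the 4 individual trajectories and one pre-specified summary per person, either baseline-to-week-12 change or slope. Give its mean and a 3-df t interval, labelled exploratory.

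**Cost.** Text edits and a simpler analysis, with no new data. The interval is wide (half-width 1.59 SD), a slope can miss an early plateau, and the t interval is only approximate if scores sit near zero. No gain in power is claimed.
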